**Section 14.3, Safety Tables**

Table 14.3.1.1	Overview of Treatment Emergent Adverse Events (TEAE)	Safety Population
Table 14.3.1.2	Treatment Emergent Adverse Events (TEAE)	Safety Population
Table 14.3.1.3	Treatment Emergent Adverse Events (TEAE) by Worst Relationship to Study Drug	Safety Population
Table 14.3.1.4	Treatment Emergent Adverse Events (TEAE) by Maximum Severity	Safety Population
Table 14.3.1.5	Treatment Emergent Adverse Events (TEAE) Leading to Discontinuation of Investigational Product	Safety Population
Table 14.3.1.6	Treatment Emergent Adverse Events (TEAE) Leading to Early Withdrawal From the Study	Safety Population
Table 14.3.1.7	Serious Treatment Emergent Adverse Events (TEAE)	Safety Population
Table 14.3.1.8	Serious Treatment Emergent Adverse Events (TEAE) by Worst Relationship to Study Drug	Safety Population
Table 14.3.1.9	Serious Treatment Emergent Adverse Events (TEAE) by Maximum Severity	Safety Population
Table 14.3.1.10	Serious Treatment Emergent Adverse Events (TEAE) Leading to Discontinuation of Investigational Product	Safety Population

REP0112

Statistical Analysis Plan

Table 14.3.1.11	Serious Treatment Emergent Adverse Events (TEAE) Leading to Early Withdrawal From the Study	Safety Population
Listing 14.3.2.1	Listing of Deaths	
Listing 14.3.2.2	Listing of Serious Adverse Events	
Listing 14.3.2.3	Listing of Adverse Events Resulting in Discontinuation of Investigational Product	
Listing 14.3.2.4	Listing of Adverse Events Leading to Early Withdrawal From the Study	
Table 14.3.4.1	Hematology	Safety Population
Table 14.3.4.2	Chemistry	Safety Population
Table 14.3.4.3	Coagulation	Safety Population
Table 14.3.4.4	Post-transplant Safety Endpoints, Excluding AST and ALT	Safety Population
Table 14.3.4.5	Post-transplant Safety Endpoints, AST and ALT	Safety Population
Table 14.3.4.6	Albumin and Pre-albumin	Safety Population
Table 14.3.5	Vital Signs	Safety Population
Table 14.3.6	Weight	Safety Population
Table 14.3.7	Steatorrhea Severity	Safety Population
Table 14.3.8	Malnutrition Risk Level	Safety Population
Table 14.3.9	Cumulative Number of Documented Symptomatic Hypoglycemic Episodes From Days 75 to 365 Following Islet Auto-transplantation	Safety Population
Table 14.3.10	Cumulative Number of Asymptomatic Hypoglycemic Episodes From Days 75 to 365 Following Islet Auto-transplantation	Safety Population
Table 14.3.11	Cumulative Number of Diabetic Ketoacidosis-related Events From Days 75 to 365 Following Islet Auto-transplantation	Safety Population

**Section 14.3, Exploratory Tables**

Table 14.3.12	Inflammatory Chemokines / Cytokines	Safety Population
Table 14.3.13	miR-375	Safety Population

**Section 14.4, Figures**

Figure 14.4.1.1	Bar Chart of Proportion of Insulin-independent Patients at Day 365 Following Islet Auto-Transplantation	Intent to Treat Population
Figure 14.4.1.2	Bar Chart of Proportion of Insulin-independent Patients at Day 365 Following Islet Auto-Transplantation	Per Protocol Population
Figure 14.4.2.1	Time Course of Glucose (unit) at Day 75, Least Squares Means Over Time	Intent to Treat Population
Figure 14.4.2.2	Time Course of Glucose (unit) at Day 75, Least Squares Means Over Time	Per Protocol Population
Figure 14.4.3.1	Time Course of Glucose (unit) at Day 365, Least Squares Means Over Time	Intent to Treat Population
Figure 14.4.3.2	Time Course of Glucose (unit) at Day 365, Least Squares Means Over Time	Per Protocol Population

REP0112

Statistical Analysis Plan

Figure 14.4.4.1	Time Course of C-peptide (unit) at Day 75, Least Squares Means Over Time	Intent to Treat Population
Figure 14.4.4.2	Time Course of C-peptide (unit) at Day 75, Least Squares Means Over Time	Per Protocol Population
Figure 14.4.5.1	Time Course of C-peptide (unit) at Day 365, Least Squares Means Over Time	Intent to Treat Population
Figure 14.4.5.2	Time Course of C-peptide (unit) at Day 365, Least Squares Means Over Time	Per Protocol Population
Figure 14.4.6.1	Time Course of Insulin (unit) at Day 75, Least Squares Means Over Time	Intent to Treat Population
Figure 14.4.6.2	Time Course of Insulin (unit) at Day 75, Least Squares Means Over Time	Per Protocol Population
Figure 14.4.7.1	Time Course of Insulin (unit) at Day 365, Least Squares Means Over Time	Intent to Treat Population
Figure 14.4.7.2	Time Course of Insulin (unit) at Day 365, Least Squares Means Over Time	Per Protocol Population
Figure 14.4.8	Post-transplant Safety Endpoints, Excluding AST and ALT, Box Plots Over Time	Safety Population
Figure 14.4.9	Post-transplant Safety Endpoints, AST and ALT, Box Plots Over Time	Safety Population
Figure 14.4.10	Albumin and Pre-albumin, Box Plots Over Time	Safety Population
Figure 14.4.11	Inflammatory Chemokines / Cytokines, Box Plots Over Time	Safety Population
Figure 14.4.12	Inflammatory Chemokines / Cytokines, Area Under the Curve Versus Total Reparixin Dose Received	Safety Population
Figure 14.4.13	Inflammatory Chemokines / Cytokines, Peak Level Versus Total Reparixin Dose Received	Safety Population
Figure 14.4.14	Inflammatory Chemokines / Cytokines, Maximum Change From Baseline Versus Total Reparixin Dose Received	Safety Population
Figure 14.4.15	miR-375, Box Plots Over Time	Safety Population

**Section 16.2, Listings**

Listing 16.2.1.1	Screen Failure and Randomization
Listing 16.2.1.2	Disposition – End of Study
Listing 16.2.2.1	Inclusion and Exclusion Criteria
Listing 16.2.2.2	Protocol Deviations
Listing 16.2.3	Patient Evaluability
Listing 16.2.4.1	Informed Consent, Demography, and Childbearing Potential
Listing 16.2.4.2	Specific Clinical History
Listing 16.2.4.3	Significant Medical History
Listing 16.2.4.4	Renal Reserve at Screening
Listing 16.2.4.5	Concurrent Sepsis at Screening
Listing 16.2.4.6	Portal Hypertension (Pre-operative) at Screening
Listing 16.2.4.7	Hospital Admission and Surgery Details
Listing 16.2.4.8	Islet Information and Pre-transplant Laboratory Draws
Listing 16.2.4.9	Transplant Details

REP0112

Statistical Analysis Plan

Listing 16.2.4.10	Post-transplant Glycemic Control
Listing 16.2.4.11	Hospital Discharge
Listing 16.2.4.12	Prior and Concomitant Medications
Listing 16.2.5.1	Investigational Product Administration
Listing 16.2.5.2	Investigational Product (IP) Administration Failure and Termination of Drug Infusion
Listing 16.2.6.1	Follow-up Visits, Part 1
Listing 16.2.6.2	Follow-up Visits, Part 2
Listing 16.2.6.3.1	Mixed Meal Tolerance Test
Listing 16.2.6.3.2	Mixed Meal Tolerance Test, C-peptide Area Under the Curve (AUC)
Listing 16.2.6.4	Patient Diary Card
Listing 16.2.6.5	$\beta$ -cell Function
Listing 16.2.6.6	Hypoglycemic Episodes
Listing 16.2.7.1	Adverse Events
Listing 16.2.7.2	Death Report
Listing 16.2.8.1.1	Laboratory Results, Hematology – Hematocrit
Listing 16.2.8.1.2	Laboratory Results, Hematology – Hemoglobin
Listing 16.2.8.1.3	Laboratory Results, Hematology – Platelet Count
Listing 16.2.8.1.4	Laboratory Results, Hematology – Red Blood Cells
Listing 16.2.8.1.5	Laboratory Results, Hematology – White Blood Cells
Listing 16.2.8.1.6	Laboratory Results, Hematology – Differential White Blood Cell Count
Listing 16.2.8.1.7	Laboratory Results, Hematology – Neutrophils
Listing 16.2.8.1.8	Laboratory Results, Hematology – Lymphocytes
Listing 16.2.8.1.9	Laboratory Results, Hematology – Monocytes
Listing 16.2.8.1.10	Laboratory Results, Hematology – Eosinophils
Listing 16.2.8.1.11	Laboratory Results, Hematology – Basophils
Listing 16.2.8.2.1	Laboratory Results, Chemistry and Coagulation – Sodium
Listing 16.2.8.2.2	Laboratory Results, Chemistry and Coagulation – Potassium
Listing 16.2.8.2.3	Laboratory Results, Chemistry and Coagulation – Blood Urea Nitrogen
Listing 16.2.8.2.4	Laboratory Results, Chemistry and Coagulation – Serum Creatinine
Listing 16.2.8.2.5	Laboratory Results, Chemistry and Coagulation – Total Bilirubin
Listing 16.2.8.2.6	Laboratory Results, Chemistry and Coagulation – Alanine Aminotransferase
Listing 16.2.8.2.7	Laboratory Results, Chemistry and Coagulation – Aspartate Aminotransferase
Listing 16.2.8.2.8	Laboratory Results, Chemistry and Coagulation – Albumin
Listing 16.2.8.2.9	Laboratory Results, Chemistry and Coagulation – Pre-albumin
Listing 16.2.8.2.10	Laboratory Results, Chemistry and Coagulation – Activated Partial Thromboplastin Time
Listing 16.2.8.2.11	Laboratory Results, Chemistry and Coagulation – International Normalized Ratio
Listing 16.2.8.3	Post-transplant Assessments – Safety Endpoints
Listing 16.2.8.4	Post-transplant Assessments – Renal Function and Total Bilirubin
Listing 16.2.9	Vital Signs
Listing 16.2.10	Post-transplant Follow-up Visits – Safety Endpoints

REP0112

*Statistical Analysis Plan*

Listing 16.2.11	Diabetic Ketoacidosis Episodes
Listing 16.2.12	Post-transplant Sampling Storage for Centralized Assay
Listing 16.2.13	Inflammatory Chemokines/Cytokines
Listing 16.2.14	Inflammatory Chemokines/Cytokines, Response Measures
Listing 16.2.15	miR-375
Listing 16.2.16	Pharmacokinetic Sampling – Blood

REP0112

Addendum to Statistical Analysis Plan

## GLOSSARY OF ABBREVIATIONS

ADIR	Average Daily Insulin Requirements
AUC	Area Under the Curve
HbA1c	Glycated hemoglobin
Kg	Kilogram
IAT	Islet Auto-Transplantation
IEQ	Islet Equivalent
ITT	Intent to Treat
MMTT	Mixed Meal Tolerance Test
PP	Per Protocol
SAP	Statistical Analysis Plan

REP0112

Addendum to Statistical Analysis Plan

## 1 INTRODUCTION

This addendum to the statistical analysis plan (SAP) for Dompé farmaceutici S.p.A (Dompé) Protocol REP0112 describes the statistical methods to be used for analysis and reporting which are to be performed in addition to those described in the SAP.

The addendum to the SAP will be finalized and approved by the sponsor in addition to the statistician of the contract research organization appointed by Dompé prior to database lock.

## 2 DEFINITIONS AND DERIVED VARIABLES

Area Under the Curve (AUC), C-peptide: When C-peptide values are below the limit of detection (0.05 ng/mL), a value equal to the limit of detection will be assumed in the calculation of area under the curve. Missing C-peptide values will be imputed via linear interpolation, and the average of the two basal samples (values, and mid-point of sample times) will be used as the first sample in the computation of the AUC. Once these rules have been applied to the data, AUC for C-peptide will be computed using the trapezoidal rule. For ease of interpretation, the AUC value obtained will be divided by the total time the scale is assessed for reporting purposes. Computation of AUC will be based on actual collection times, unless actual collection time is missing, in which case the scheduled collection time will be used.

AUC0-72H, miR-375: Missing miR-375 values will be imputed via linear interpolation. Once these rules have been applied to the data, AUC0-72H for miR-375 will be computed using the trapezoidal rule. Computation of AUC0-72H will be based on actual collection times, unless actual collection time is missing, in which case the scheduled collection time will be used.

Other definitions and derived variables are found within the applicable subsections of Section 3, Statistical Methods.

## 3 STATISTICAL METHODS

### 3.1 Methods for Multiplicity Correction in Analyses

All efficacy endpoints planned in this addendum are exploratory in nature and will be tested without a multiplicity correction being applied. In addition, all efficacy endpoints planned in the SAP will also be interpreted without the planned conditional sequential multiplicity correction being applied.

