#### **9.4. STATISTICAL METHODOLOGY**

All patient data collected on the CRF and on the Diary will be listed by patient, treatment group and centre.

Appropriate descriptive statistics will be produced, according to the variable. For continuous variables, the data will be presented according to a clinically relevant discretization. For categorical data, frequencies and percentages will be presented. If appropriate, confidence intervals around the mean or the proportions will be presented.

All the AUC analyses will be based on actual rather than scheduled timings and will be calculated using the trapezoidal rule. If the actual time is not recorded, the scheduled time will be used instead. For ease of interpretation, the AUC value obtained will be divided by the total time the scale is assessed for reporting purposes.

The data will be presented in the Clinical Study Report. A Statistical Analysis Plan will be issued describing details of all the statistical methods and analyses to be applied to trial results, including alpha spending and testing for multiple endpoints. Any deviations from the original statistical plan will be described in the Clinical Study Report.

All reasonable efforts will be made to prevent missing data. Thoughtful methods for imputation of missing data will be presented in the Statistical Analysis Plan for the clinical trial

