#### **9.4.7. Methods for multiplicity correction in analyses**

If the primary analysis of the primary endpoint leads to rejection of the null hypothesis, the null hypotheses for the secondary endpoints will be tested in a conditional sequential manner. A null hypothesis will be rejected if and only if the primary analysis of that endpoint and all primary analyses of preceding primary and secondary endpoints result in a rejection of the respective null hypotheses. This procedure protects the family-wise false positive error rate at the overall one-sided 0.025 level.

It is noted that for secondary endpoints that will be tested both at  $75\pm14$  and  $365\pm14$  days after the transplant, only the day  $365\pm14$  time point will be tested for superiority in the fixed sequence testing procedure.

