## 7 STATISTICAL METHODS

### 7.1 General Principles

The statistical package SAS® will be used to produce all summary tables, figures, and listings.

In general, categorical data will be presented using counts and percentages, whilst continuous variables will be presented using the number of patients, mean, standard deviation, median, minimum, and maximum. Denominators for calculation of percentages will be taken as the number of non-missing responses in the specified analysis population and treatment group unless otherwise stated, and percentages will be rounded to one decimal. Minima and maxima will usually be reported to the same level of accuracy as the raw data; means, medians and standard deviations will be presented to one further decimal place; standard errors (if presented) will be presented to 2 decimal places more than the raw data.

REP0112

Statistical Analysis Plan

All data recorded in the CRF will be listed.

Unless otherwise specified, the significance level used for statistical testing will be 5% and two-sided tests will be used.

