## 7.3 Methods for Multiplicity Correction in Analyses

If the primary analysis of the primary endpoint leads to rejection of the null hypothesis, the null hypotheses for the following secondary endpoints will be tested in a conditional sequential manner. The sequence in which these secondary endpoints will be tested is as follows:

1. AUC for serum C-peptide level during the first 4 hours of a MMTT, normalized by the number of IEQ/kg, at Day 365 ± 14 days after IAT.
2. Average daily insulin requirement at Day 365 ± 14 days after IAT.
3. Time course of C-peptide derived from the MMTT at Day 365 ± 14 days after IAT.
4. β-cell function as assessed by β-score at Day 365 ± 14 days after IAT.
5. The proportion of patients with HbA1c ≤ 6.5% at Day 365 ± 14 days after IAT.

REP0112

Statistical Analysis Plan

6. Cumulative number of severe hypoglycemic events from Day 75 ± 14 days to Day 365 ± 14 days after IAT.
7. The proportion of patients with HbA1c ≤ 6.5% at Day 365 ± 14 days after IAT **AND** free of severe hypoglycemic events from Day 75 ± 14 days to Day 365 ± 14 days after IAT, inclusive.

A null hypothesis will be rejected if and only if the primary analysis of that endpoint and all primary analyses of preceding primary and secondary endpoints result in a rejection of the respective null hypotheses. This procedure protects the family-wise false positive error rate at the overall one-sided 0.025 level.

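### Addendum 3.1 drops the fixed testing sequence for the SAP's secondary endpoints and puts nothing in its place, while the protocol and SAP still claim one-sided 0.025 family-wise control

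*SAP*

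**What the plan says.** Protocol 9.4.7 makes the primary endpoint a gate. If it succeeds, "the null hypotheses for the secondary endpoints will be tested in a conditional sequential manner". The protocol gives no order, and its section 9.4 leaves the detail to the SAP, "including alpha spending and testing for multiple endpoints".

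SAP 7.3 repeats the gate and supplies the order ("The sequence in which these secondary endpoints will be tested is as follows"), listing seven secondaries:

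1. C-peptide AUC normalized by IEQ/kg
2. average daily insulin requirement
3. C-peptide time course
4. β-score
5. HbA1c ≤6.5%
6. severe hypoglycemic events
7. HbA1c ≤6.5% with no severe hypoglycemic event

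It closes with "This procedure protects the family-wise false positive error rate at the overall one-sided 0.025 level". Protocol 9.4.7 makes the same statement.

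The SAP Addendum introduces its analyses as ones "which are to be performed in addition to those described in the SAP". Its section 3.1 has two sentences. The first concerns its own endpoints: "All efficacy endpoints planned in this addendum are exploratory in nature and will be tested without a multiplicity correction being applied". The second reaches back into the SAP and says that "all efficacy endpoints planned in the SAP will also be interpreted without the planned conditional sequential multiplicity correction being applied".

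The default in SAP 7.1 is that "the significance level used for statistical testing will be 5% and two-sided tests will be used". The primary test is one-sided at 2.5% (SAP 7.5.1).

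**The concern.** The 0.025 family-wise figure is a property of the sequence. Once the sequence is not applied, the figure no longer describes the plan, yet neither the protocol nor the SAP withdraws it. The addendum calls its own endpoints exploratory but does not say this of the seven SAP secondaries, so their status is unclear and each can be read at its own two-sided 5% level.

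The case that matters is a failed primary with a secondary at p<0.05. Protocol 9.4.7 and SAP 7.3 forbid a claim; Addendum 3.1 removes the rule that forbids it. The same data could then support opposite conclusions depending on which document is followed. C-peptide AUC is the obvious candidate, since the sample-size sections call it the key secondary endpoint and give power for it. Someone who reads only the protocol would believe the error rate is controlled.

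**Working it through.** **Inputs from the documents.** Seven ordered secondaries, eight hypotheses with the primary (SAP 7.3). The primary is tested at one-sided 0.025 (SAP 7.5.1). Each secondary is tested at two-sided 0.05, which is 0.025 in the direction favouring reparixin (SAP 7.1 and 7.5.2). Stated family-wise error: one-sided 0.025.

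**Assumed, because the documents give no figure.** The test statistics are jointly normal with a common correlation ρ between every pair, and there is no effect on any endpoint.

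**The plan's own figure.** With the fixed sequence and no effect anywhere, a false claim requires the first test to reject. The rate is P(primary rejects) = 0.025 at any correlation. The stated figure is reproduced.

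**Without the sequence.** For k tests, the chance of at least one rejection favouring reparixin is:

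- independent tests: 1 − 0.975^k
- correlation ρ: 1 − ∫ φ(x) · Φ[(1.96 − √ρ·x)/√(1−ρ)]^k dx, evaluated numerically

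For independent tests, 1 − 0.975^7 = 0.162 and 1 − 0.975^8 = 0.183.

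The chance that the primary fails and at least one secondary still rejects is the eight-test rate minus 0.025. At ρ = 0 this is 0.183 − 0.025 = 0.158.

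| Assumed ρ | At least one of 7 secondaries | Primary or any secondary | Primary fails, at least one secondary rejects |
|---|---|---|---|
| 0 | 16.2% | 18.3% | 15.8% |
| 0.3 | 13.7% | 15.2% | 12.7% |
| 0.5 | 11.5% | 12.5% | 10.0% |
| 0.7 | 8.9% | 9.5% | 7.0% |
| 0.9 | 5.7% | 6.0% | 3.5% |
| SAP 7.3 sequence, any ρ | at most 2.5% | 2.5% | 0% |

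**Allowing for overlap.** Endpoints 1 and 3 both come from the C-peptide curve, and 5 and 7 share the HbA1c criterion. Simulation with those two pairs at an assumed 0.9 and all other correlations at 0.3, 0.5 or 0.7 gives about 12%, 10.4% and 8.4% for the seven secondaries. For a failed primary with at least one secondary rejecting it gives 11.1%, about 9% and 6.6%.

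Only perfect correlation brings the rate back to 2.5%.

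**The case against.** The best defence is that Addendum 3.1 is open about what it does. It names the sequential correction and says it will not be applied, so a reader of the SAP and addendum together is not deceived. The error-control sentence is tied to the procedure and could be taken to lapse with it. Coming straight after a sentence about exploratory endpoints, the second sentence could also mean that the SAP secondaries are now nominal. The protocol leaves multiplicity detail to the SAP and provides for deviations to be described in the study report. The addendum was due before database lock, and the trial is called a pilot.

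Some of this stands. The primary keeps its one-sided 0.025 level and no data-driven change is alleged. The Day 75 results and the glucose and insulin time courses were never in the sequence, so nothing is lost there. The rates depend on assumed correlations, and because the endpoints overlap the top of the range is unlikely. Addendum 3.2.1, on the primary variable, is not in the text available for review, although the multiplicity section is.

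The rest does not settle the matter. The nominal reading rests on the wording linking the two sentences, not on any stated status for the SAP secondaries. Addendum 3.2 still describes its per-protocol efficacy analysis as confirmatory. The protocol itself, not only the SAP, fixes the gate and the 0.025 claim. Describing a deviation in the study report does not decide beforehand which rule governs.

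**Conclusion.** The concern holds. Taken together, the documents state an error property that the plan no longer has, and they do not determine whether a secondary can be claimed after a failed primary. What is lost is control over the primary and seven secondaries jointly.

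Against the stated 2.5%, the joint rate is 6.0% to 18.3% over the assumed correlations, which is more than double even at 0.9. The overlap scenario, about 12% to 8.4% for the secondaries alone, is the more realistic guide. These figures assume no effect on any endpoint, normal statistics and the stated correlations. The contradiction between the texts needs none of those assumptions, and it should be resolved before database lock.

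**What to change.** **Option A, preferred.** Delete the second sentence of Addendum 3.1 and keep the SAP 7.3 sequence. Report p-values after the first non-rejection as nominal, and leave the addendum's own endpoints exploratory. The cost is one sentence of the addendum, and secondaries after the first non-rejection lose confirmatory status. Separately, SAP 7.5.2.1 and 7.5.2.2 each give a t-test and a mixed model without saying which is the primary analysis. SAP 7.3 needs that named for steps 1 and 2, so it should be settled in the same revision.

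**Option B, if the sponsor does intend to drop the sequence.** State that only the primary endpoint is confirmatory and label every secondary nominal. Withdraw the family-wise statement from SAP 7.3 and Protocol 9.4.7. Record the departure in SAP 1.2, which now declares no changes from the protocol, and say in the addendum's introduction that it modifies SAP 7.3. The cost is SAP wording plus a protocol change, and all secondaries lose confirmatory status.

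Neither option needs new data if made before database lock.
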